### 3) Setting of the Human Research

76 volunteers will be given general anesthesia in the research imaging unit. Cognitive testing will occur prior to the administration of anesthesia and at intervals until complete cognitive recovery occurs. Cognitive

|   |   |   |
|---|---|---|
| 
Mount
Sinai | Protocol Title:                           | Trajectory of Recovery in the Elderly                                   |
|   | Principal Investigator Name/Contact Info: | [name]
[contact]                       |
|   | Primary Contact Name/Contact Info         | [name] [contact]
[contact] |
|   | Date Revised:                             | 02/23/2018  |
|   | Study Number:                             | GCO 13-0359   |
|   |   |   |

testing will also occur at 1, 7 and 30 days after the initial administration of anesthesia. The POSTOP-QRS will be conducted over the phone or in person at baseline and during recovery (while in the recovery room) and 1 day, 3 days, 7 days and 30 days and after the initial MRI with anesthesia. A POSTOP-QRS will be repeated at 6 and 12 months after your initial procedure for safety purposes.

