10.1 Specific Aim I: *The primary goal is to test whether age is associated with the time of return to baseline cognitive function, assessed by PQRS (primary) and NIH toolbox (secondary), following general anesthesia.*

Scales of the PQRS are performed prior to anesthesia, and then following anesthesia at defined time intervals (see Section 4). We will focus on the recovery of cognitive function (the primary endpoints as described in 5.0) as related to age and controlling for other participant characteristics using Cox discrete time regression.⁷⁴ We expect that everyone will return to baseline cognitive function by 30 days, most early in the course of testing. Thus, if later time points are missing most will have been observed before loss to follow-up. For intermittent missingness before returning to baseline, we will truncate the observations at the time of missing observations. In a subsequent sensitivity analysis, we will assume that they are missing at random and use last value carried forward (worse-case scenario). We will also explore multiple imputation if >5% of the outcome data are missing prior to returning to baseline function.

For the secondary NIH Toolbox outcomes, we will calculate six primary standard Adjusted Scale Scores, as described in the Scoring Manual for Toolbox measures described in 5.1. We will again use discrete time Cox regression with covariate adjustment; however, the granularity of the timing of measurements is less than the primary outcome of PQRS. For both the primary and secondary outcomes, we will use the Hochberg test to adjust for multiple comparisons.⁷⁵

To study the time course of the PQRS and Toolbox measures, we will use generalized linear mixed models (GLMMs),⁷⁶ which account for the covariance structure of repeated observations within participant, and we will test whether a random intercepts and slopes for participants best fit the data. GLMMs are statistical models for data with correlations or non-constant variability and where the response is not necessarily normally distributed. GLMMs assume that missing data are missing at random; thus, participants with partial data contribute to the model estimation. We will fit the appropriate distribution (e.g. dichotomous, count, ordinal, normal) for each outcome using Proc GLIMMIX in SAS v9.3.

10.2 Specific Aim II: *The measures for fMRI analyses generally fall into three groups: resting, task-driven, and rCBF.*

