Change scores will be calculated for each of 20-25 components (characterizing resting state and activity driven brain networks) related to fMRI imaging at each time point (Section 4). These changes (expressed in standardized units) associated with age will be analyzed using GLMMS adjusted for participant characteristics as described for Aim 1. We will use the False Discovery Rate test to adjust for multiple comparisons.⁷⁷

For the ASL analysis, an additional 5 measures for rCBF (global and right/left frontal and temporal) will be generated for each of three time points and analyzed with GLMMS corrected for multiple comparisons as described above.

fMRI components will be entered as covariates in the above-mentioned Cox discrete-time models for the primary outcomes (PQRS and NIH Toolbox scales) to assess their association with the primary outcomes and with age. Similarly, the fMRI components will be entered into the GLMMS described in 10.1 to estimate their adjusted associations. We will use the False Discovery Rate test to adjust for multiple comparisons.⁷⁷

10.3 Sample Size, Power, and Effect Size Estimation:

Sample and power for secondary outcomes were calculated with PASS12 (PASS12, Kayville, Utah, USA). **SA1:** A Cox regression⁷⁸ on the time to return to baseline cognitive performance requires 72 participants to detect a HR of 1.03 per year or age ($\beta=0.033$), assuming a standard deviation for age of 11.25 years, 80% power, a Type I error of 0.05, and adjusting for other characteristics expected to have a generalized R^2 of 0.2.⁷⁹⁸⁰

The NIH toolbox yields six primary standardized scaled scores (mean=100, SD=15). Although there will be fewer discrete time measurements for Cox regression, the effect-size calculation is similar. Assuming 72 participants with a standard deviation for age of 11.25 years, an adjusted Type 1 error rate of $0.05/6=0.0083$, and other covariates having a generalized R^2 of 0.2 with age, a HR of 1.04 ($\beta=0.041$) can be detected with 80% power.⁸⁰

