SA2: A sample size of 72 maintains 80% power for 30 MRI components to detect a change of 0.04 in each component testing for variation across the age spectrum where the assumed standard deviation of age is 11.25 years, the SD of the normalized MRI component outcomes is 1.0, and the two-sided Type I error of 0.0017 to account for multiplicity of the 30 tests (Bonferroni correction). We recognize that in fMRI, multiple comparisons across massive numbers of voxels make it extremely difficult to formulate valid assumptions regarding variability. However, we are using summary measures for these components and have used a Bonferroni adjustment for power calculation.

We expect missing data to be low as the total time under observation is 30 days and all participants are expected to have returned to baseline cognitive function by 30 days. Preliminary data had 75% return to baseline at T+15 minutes and all by 7 days. Thus, outcomes are expected to be captured on the majority of subjects even if they do not attend all follow-up visits. However, to insure sufficient outcomes we will increase by 5.5% to 76 thus adding a participant to each age decade.

11. Scientific Limitations and Rationale for Design Decisions

The results will be a first step and cannot completely elucidate age-related differences in subjects and conditions associated with clinical indications for surgery. The study focuses on the main effect of anesthesia on cognitive recovery but cannot address the possibility that administration of anesthesia interacts in some way with what happens due to the surgery itself. There are multiple anesthetics in current use. This proposal includes a fairly standard combination of anesthetic agents. Additional agents cannot be accommodated in this model. Safety is a primary concern. The current design is focused on safety as opposed to results at any cost.

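### SAP 10.3 takes its 80% power for age from an untied Cox formula; with the SAP's pilot recovery figures the planned discrete-time analysis of PQRS has about 62–74% at n=72

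*SAP*

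**What the plan says.** SAP 10.1 plans to relate PQRS recovery to age, "controlling for other participant characteristics using Cox discrete time regression". The NIH Toolbox scales get the same type of model, with the remark that "the granularity of the timing of measurements is less than the primary outcome of PQRS". On multiplicity it says "we will use the Hochberg test to adjust for multiple comparisons".

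SAP 10.3 states that a Cox regression "requires 72 participants to detect a HR of 1.03 per year or age", with beta 0.033, an age SD of 11.25 years, 80% power, type I error 0.05 and a covariate R² of 0.2. For the six Toolbox scales it uses n=72, alpha 0.05/6 = 0.0083 and beta 0.041, and comments: "Although there will be fewer discrete time measurements for Cox regression, the effect-size calculation is similar".

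The last paragraph of SAP 10.3 gives the pilot result: "Preliminary data had 75% return to baseline at T+15 minutes and all by 7 days". It uses this only to argue that little outcome data will be missing, and then raises enrolment from 72 to 76 to protect the number of outcomes.

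The data collection schedule in Protocol 5d has PQRS at T+15, T+40 and days 1, 3, 7 and 30, and again at 6 months. After anesthesia, the Toolbox row is marked only at days 1, 7 and 30. Protocol 3 agrees ("testing will also occur at 1, 7 and 30 days after the initial administration of anesthesia") but also mentions cognitive testing "at intervals until complete cognitive recovery occurs", without saying which tests.

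**The concern.** The inputs to the power calculation are beta, the SD of age, R², alpha and power. Nothing describes the visits or how recoveries spread over them. That suits exact, distinct event times. In a discrete-time model, people who recover by the same visit cannot be ordered among themselves, so the data say less about age. Here the SAP's own pilot figure places most recoveries at the first visit after anesthesia.

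This calculation is the stated basis for 72 participants in the primary aim. If it overstates power, a non-significant age result would be read against an 80% assurance that the planned model does not give.

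**Working it through.** **1. The plan's figures.** The standard Cox formula for a continuous covariate, with one untied event per participant, is

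n = (z₁₋α/₂ + z_power)² / [SD² × β² × (1 − R²)].

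- SA1: (1.960 + 0.842)² / (11.25² × 0.033² × 0.8) = 71.2, so 72.
- Toolbox, alpha 0.0083 and beta 0.041: 71.1, so 72.

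The SAP prints no formula, so its use is an inference. Two separate figures support it, and variants of the SA1 calculation do not give 72: one-sided alpha gives 57, omitting R² gives 57, and ln(1.03) in place of 0.033 gives 89. By this formula, power is 80.4% at n=72 and 82.5% at n=76.

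**2. Allowing for visits.** Under grouped proportional hazards (complementary log-log link), the information per participant relative to one exact event is

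I = Σ over visits of S × (1 − h) × [ln(1 − h)]² / h,

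where S is the share not yet recovered and h is the fraction of those who recover at that visit. The visit at which the last participants recover adds 0. Then

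power = Φ( √[n × I × SD² × β² × (1 − R²)] − z₁₋α/₂ ).

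**3. PQRS.** At T+15, S = 1 and h = 0.75, which contributes 0.25 × (ln 0.25)² / 0.75 = 0.641. The documents do not say how the remaining 25% divide among T+40 and days 1, 3 and 7, so the split is varied. For an even split over two visits, for example, the first adds 0.25 × 0.5 × (ln 0.5)² / 0.5 = 0.120, giving I = 0.761.

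| Later 25% recover | I | Power, n=72 | Power, n=76, no loss |
|---|---|---|---|
| All at one visit | 0.641 | 62% | 64% |
| Evenly over two visits | 0.761 | 69% | 71% |
| Evenly over three | 0.803 | 71% | 74% |
| Evenly over four | 0.824 | 73% | 75% |
| 15/5/3/2% | 0.857 | 74% | 76% |
| Most informative split over four | 0.863 | 74% | 77% |
| Exactly timed, no ties (a bound, not attainable) | 0.641 + 0.25 = 0.891 | 76% | 78% |

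Worked case, first row: 72 × 0.641 × 11.25² × 0.033² × 0.8 = 5.09; √5.09 − 1.96 = 0.295; Φ(0.295) = 0.62.

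The hazard ratio detectable with 80% power at n=72 is exp{2.802 / √[72 × I × 11.25² × 0.8]}. This is 1.042 for I = 0.641 and 1.036 for I = 0.863, against 1.033 for I = 1. At n=76 the range is 1.035–1.041.

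**4. Sensitivity.** With 65–85% recovered at T+15 instead of 75%, power at n=72 is 58–76%. If the T+15 share is left free and all recover by day 7, the ceiling is 77.4% at n=72 and 79.6% at n=76. If recovery may run to day 30, the ceilings are 78.3% and 80.5%, but that pattern needs only 39% recovered at T+15.

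**5. Simulation check.** Trials were simulated with uniform age (SD 11.25), one covariate with R² 0.2, and 1,500 trials per scenario. The complementary log-log fit gave about 59–71% at n=72 and 59–74% at n=76; a logit fit to the same data gave about 56–68% and 58–71%. A near-continuous control at n=72 (300 trials) gave 81%, so ties account for the loss.

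**6. Toolbox.** No recovery rate is given, so only ceilings can be stated, maximising I over all patterns at days 1, 7 and 30 (alpha 0.0083, beta 0.041):

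- All recovered by day 30: I ≤ 0.820, power at most 70% at n=72 (73% at n=76).
- Any pattern, including some never recovering: I ≤ 0.891, at most 75% (78%).
- One or two extra test times, any pattern, n=72: at most 77% or 78%.

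Under Hochberg, power per affected scale depends on how many of the six scales carry the effect. This was computed at n=72 with 200,000 draws and common correlations from 0 to 0.9:

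| Scales affected | At I = 0.820 | At I = 0.891 | No-ties formula |
|---|---|---|---|
| One | 70% | 75% | 80–81% |
| Three | 73–74% | 77–78% | 83–84% |
| Six | 82–85% | 85–88% | 90–92% |

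**The case against.** - **The model is not fully specified.** SAP 10.1 names no link, and the 62–74% takes 0.033 as a log hazard ratio. This stands as a condition, but the alternatives do not help the plan. With proportional hazards a logit link gives no more information (0.796 against 0.824 for the even four-visit split). Reading 0.033 as a per-visit log odds ratio gives only about 23–35% at n=72.
- **The pilot figure is thin.** The SAP gives no pilot size, does not name the instrument and does not split the later 25%. PQRS is a fair inference, because in the schedule only PQRS is done at T+15. The 62% end needs every later recovery at a single visit; splits over two or more give 69–74%. So the endpoints are conditional, but the conclusion is not: even exactly timed later recoveries give 76% at n=72.
- **The formula is approximate.** True, but the simulations fall below it by up to about five points, so the range is if anything generous.
- **The Toolbox point is weaker.** Protocol 3 leaves test times open, and under Hochberg the ceilings fall on both sides of 80%. This stands. What fails is the claim of a similar calculation at alpha 0.0083 if testing is at days 1, 7 and 30.
- **The practical shift is modest.** The detectable hazard ratio moves from about 1.033 to 1.036–1.042. The SAP's rounding matters about as much: using ln(1.03) instead of 0.033 cuts its own formula's power at n=72 from 80.4% to 71.4%. Also, a null result should be read from its confidence interval. These points bear on how large the remedy should be. They do not make the stated 80% correct.

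**Conclusion.** The concern holds. The stated 80% belongs to a continuous-time analysis without ties, and nothing in the documents allows for the grouping that the planned model and the pilot figures imply. The increase to 76 was made for missing outcomes and does not close the gap.

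The direction is firm. The exact PQRS range rests on 75% recovered at T+15, all recovered by day 7, proportional hazards and an assumed split of the later recoveries. The Toolbox conclusion is limited to alpha 0.0083 with testing at days 1, 7 and 30. The point should be fixed, but it does not call the design or the analysis into question.

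**What to change.** Keep the sample size and the analysis. In SAP 10.3:

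- Restate SA1 power, or the detectable hazard ratio, for the actual PQRS visits. Give the recovery pattern as an explicit assumption: 75% at T+15, with a range of splits for the rest. Name the link.
- Do the same for the Toolbox over a range of recovery rates, and state its test times.
- Say whether Toolbox power refers to alpha 0.0083 or to Hochberg and, if Hochberg, how many scales are assumed to carry the effect.
- Delete the remark that the Toolbox calculation is similar.

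The cost is SAP wording and a short calculation, with no extra participants. The only drawback is a less favourable stated power.
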